## 5. RATIONALE AND BACKGROUND

Cabotegravir (CAB), an HIV-1 integrase strand transfer inhibitor (INSTI), in combination with rilpivirine (RPV), an HIV-1 NNRTI, is indicated as a complete regimen for the treatment of HIV-1 infection in adults who are virologically suppressed (HIV-1 RNA < 50 copies /mL) on a stable ART regimen without present or past evidence of viral resistance to, and no prior virological failure with CAB or RPV (in the US)/agents of the NNRTI and INI class (in Europe).

The novel long-acting ART delivered through intramuscular injection—CAB+RPV LA—has been shown to be non-inferior to daily oral therapy. Before starting the regimen, the healthcare provider should carefully select people with HIV who agree to the required injection schedule and counsel individuals about the importance of adherence to scheduled dosing visits to help maintain viral suppression and reduce the risk of viral rebound and potential development of resistance associated with missed doses. After discontinuation of CAB+RPV LA injection, it is essential to adopt an alternative, fully suppressive ARV regimen.

CAB in combination with RPV has a prolonged pharmacokinetic tail, which presents individuals with the opportunity to take their HIV treatment once monthly or once every 2 months instead of daily, potentially allowing for much improved adherence. While clinical studies have established the efficacy, safety, and tolerability of CAB+RPV LA, this study will assess global utilization patterns, adherence, persistence, discontinuation, effectiveness, and resistance among virologic failures with available resistance testing data, as well as patient-reported outcomes of this regimen in a real-world clinical setting.

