## 6.2. Secondary Objectives

1. Subgroup analyses by BMI (< 30, ≥ 30-<40 and ≥40 kg/m^2) at initiation, age at initiation (18-49, 50-64, ≥ 65 years), sex assigned at birth (female, male), race and ethnicity, sex/race, and country, if sample sizes allow, to assess characteristics, adherence, persistence, discontinuation, and virologic effectiveness
  
2. To estimate the frequency of documented injection site reactions and

hypersensitivity reactions among participants receiving CAB+RPV LA injections

3. To describe resistance and ART regimen among participants after discontinuation/CVF of CAB+RPV LA, where VL data are available and resistance testing has been done as part of routine clinical practice
  - Describe resistance (where this has been done as part of routine clinical practice) at the time of discontinuation/CVF and history of resistance and proviral DNA testing before discontinuation/CVF
  - Describe the ART regimen and virologic outcomes after discontinuation/CVF of CAB+RPV LA
    - To describe the demographic and clinical characteristics of participants who continue to stay on CAB+RPV LA as compared to those who switched regimens after discontinuation or CVF
    - To describe virologic response (suppression, non-response, CVF) to ART regimen after discontinuation/CVF of CAB+RPV LA
4. To describe reasons for initiating CAB+RPV LA, health-related quality of life, treatment satisfaction, treatment preference, treatment-related stigma, benefits, and reasons for missed injections and discontinuation among prospective participants (new initiators) of CAB+RPV LA
5. For data collected beyond the two-year follow-up period, outcomes will be analyzed at the extended time points

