### Prospective Participants:

[figure not shown]
Prospective participants will include individuals enrolled from November 2025 until study size is reached. Participants will be enrolled prior to their first CAB+RPV LA injection, either during the optional oral lead-in (OOLI) phase, if applicable, or directly before their first CAB+RPV LA injection for those on the direct-to-injection (DTI) pathway. The baseline survey will be administered before the first CAB+RPV LA injection. The participants will be followed for a minimum of two years, unless they withdraw from the study, are lost to follow-up, or pass away. Participants who discontinue and switch to a subsequent regimen or who experience CVF will be followed-up for a minimum of 6 months and may be extended until viral load assessment is completed, with a maximum duration of 12 months.

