	Q2M 2 nd initiation injection	Q2M continuation injection																
On-time	23-37	53-67																
Late	38-67	68-127																
Delayed (Short delay)	38-67	68-97																

Endpoint	Definition		
	Long delay (requiring re-initiation)	NA	98-127
	Requiring re-initiation/ Discontinuation	>67	>127
CVF	Proportion of participants with: 
 
▪ 2 consecutive HIV RNA VL <math>\geq</math> 200 copies/mL prior to/by assessment timepoint
 
OR
 
▪ 1 HIV RNA VL level <math>\geq</math> 200 copies/mL prior to/by assessment timepoint followed by core agent/regimen discontinuation within 4 months of HIV RNA VL level <math>\geq</math> 200 copies/mL
 
		
Virologic suppression	
 
▪ Proportion of participants with VL measurement <math><</math> 50 copies/mL during follow-up
 
		
Non-response	
 
▪ Not achieving re-suppression after CVF, consisting of VL <math>\geq</math>50 copies/mL following CVF with no VL of <math><</math>50 copies/mL following CVF
 
		
Secondary			
Injection site reactions	
 
▪ Proportion of participants with documented diagnostic code/diagnosis of injection site reaction or nodules attributed to administration of CAB+RPV LA
 
▪ Proportion of participants with Division of AIDS grading 1-4 to classify severity
 
		
Hypersensitivity reactions	
 
▪ Proportion of participants with documented diagnosis of Hypersensitivity, anaphylactic reaction, allergic reaction or drug allergy to CAB+RPV LA
 
▪ 2 or more events are reported from 2 or more of the following groups of signs/symptoms:                             
 
○ Rash, fever, gastrointestinal symptoms (nausea, vomiting, diarrhea, abdominal pain), constitutional symptoms (lethargy, fatigue, malaise, myalgia, arthralgia, general ill feeling) respiratory symptoms (dyspnea, sore throat, cough, chest x-ray changes, predominantly infiltrates, which can be localized)
 
 
 
▪ Cases where there is a negative rechallenge with CAB+RPV LA
 
▪ Cases where symptoms resolved (or did not worsen/result in withdrawal from the study)
 
		

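### Non-response is defined only after CVF, so participants who stop CAB+RPV LA without CVF and are unsuppressed on the next regimen, short of CVF, have no category under secondary objective 3

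*Protocol*

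**What the plan says.** Section 6.2, item 3, sets the task: "To describe virologic response (suppression, non-response, CVF) to ART regimen after discontinuation/CVF of CAB+RPV LA". The population is everyone who leaves CAB+RPV LA, with or without CVF. Section 7.3.2 defines the three classes:

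- **Suppression:** "Proportion of participants with VL measurement" below 50 copies/mL during follow-up. No earlier failure is required.
- **CVF:** either "2 consecutive HIV RNA VL" results of 200 copies/mL or more, or one such result "followed by core agent/regimen discontinuation within 4 months of HIV RNA VL level" of 200 or more. Neither limb is restricted to time on CAB+RPV LA, and section 6.2 names CVF as a possible response to the next regimen.
- **Non-response:** "Not achieving re-suppression after CVF, consisting of VL" of 50 copies/mL or more, with no result below 50. Both conditions are counted from CVF.

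For participants who switch or have CVF, section 7.2 uses the same follow-up rule in the prospective and retrospective groups: they are "followed-up for a minimum of 6 months and may be extended until viral load assessment is completed, with a maximum duration of 12 months". Section 7.1 leaves laboratory testing to the treating physician, so no VL schedule applies.

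**The concern.** The objective and the definition cover different populations. The objective applies non-response to all who discontinue; the definition admits only those with an earlier CVF. Someone who stops CAB+RPV LA while suppressed, and then has a VL of 120, or a single VL of 500 without stopping the new regimen, is not suppressed, has not met CVF and cannot be a non-responder.

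At stake is the completeness of one descriptive table. The unclassified results are all unsuppressed ones, and all fall among participants who stopped for reasons other than CVF. A reader of the non-response count would not know that this group was never eligible for it.

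The gap is more likely to show when only one VL is available, because the two-result limb of CVF then cannot be met. Section 7.2 allows this: if no VL is taken in the first 6 months, the extension may end with the first one.

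**Working it through.** **The plan's own figure.** The only statistical figure in the protocol is the precision statement in section 7.5: exact 95% interval widths of 1.28% and 2.13% for failure rates of 2% and 6% with N = 2,000. With the Clopper-Pearson limits, lower = Beta(0.025; x, n−x+1) and upper = Beta(0.975; x+1, n−x):

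- x = 0.02 × 2,000 = 40: 0.0143 to 0.0271, width 0.0128.
- x = 0.06 × 2,000 = 120: 0.0500 to 0.0713, width 0.0213.

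Both agree with the protocol. The present point concerns definitions and does not depend on them.

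**Inputs for the check.** Three VL bands (<50, 50–199, ≥200 copies/mL), prior CVF or not, and whether the next regimen is stopped within 4 months of a VL ≥200. Every sequence of one or two VLs after the switch is classified by the section 7.3.2 definitions.

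**One VL on the next regimen:**

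| VL | Prior CVF | No prior CVF |
|---|---|---|
| <50 | suppression | suppression |
| 50–199 | non-response | **none** |
| ≥200, regimen not stopped within 4 months | non-response | **none** |
| ≥200, regimen stopped within 4 months | CVF and non-response | CVF |

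Without a stop, 2 of the 3 bands are unclassified for participants with no prior CVF.

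**Two VLs, no stop, no prior CVF** (3 × 3 = 9 patterns):

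- At least one VL <50: 9 − (2 × 2) = 5 patterns, all suppression.
- ≥200 twice: 1 pattern, CVF.
- 50–199 twice, 50–199 then ≥200, ≥200 then 50–199: 9 − 5 − 1 = 3 patterns, no class.

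For participants with prior CVF, every pattern containing at least one VL has a class.

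**After rewording.** If non-response is counted after discontinuation or CVF, the unclassified patterns fall from 2 of 3 to 0 of 3 (one VL) and from 3 of 9 to 0 of 9 (two VLs). A participant with ≥200 twice, or ≥200 and a stop, then meets both CVF and non-response. That overlap already exists for participants with prior CVF, so the wording should give CVF its own class.

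**The case against.** The best defence is that the definition suits its evident purpose. Non-response means failing to regain suppression, which fits people who lost it through CVF; someone who stops while suppressed has nothing to regain, and failure of the next regimen is CVF. This explains the wording but does not remove the mismatch, since section 6.2 lists non-response for discontinuation as well as for CVF.

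The defence does stand against several stronger readings:

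- **Failure of the next regimen cannot be recorded.** A reader might infer this, but either CVF limb can record it, including the one that needs only a single VL and a regimen stop.
- **Secondary objective 3 cannot be answered.** Resistance, subsequent regimen, the comparison of those who stay with those who switch, suppression, CVF and non-response after CVF all remain describable. One class is undefined for one subgroup.
- **Suppression is biased upward.** An unclassified participant is not in the suppression numerator, and nothing in section 7.3.2 removes that participant from the denominator. The bias would arise only if a table dropped the unclassified, which the protocol does not say.
- **Follow-up closes at the first VL.** The 6-month minimum stands regardless, and several routine VLs may fall within it. A single VL is possible, not the rule.
- **Residual drug makes early suppression look like response.** Section 5 says that "CAB in combination with RPV has a prolonged pharmacokinetic tail", but gives no duration and no effect on VL under a new regimen. VL windows may also be set in a statistical analysis plan that is not shown.

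**Conclusion.** The point holds in a narrow form. Sections 6.2 and 7.3.2 disagree on who can be a non-responder. Followed exactly, the protocol leaves non-CVF discontinuers unclassified when they are unsuppressed on the next regimen without meeting CVF: VL of 50–199 with none below 50, or an unconfirmed VL ≥200 with no stop within 4 months. The non-response count omits them.

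The number of participants cannot be derived, because the protocol gives no discontinuation rate and no VL distribution after switching. A reader might try to size it from the 2–6% failure range in section 7.5 (40–120 of 2,000). Assuming that 15–25% discontinue (300–500) and that all CVF cases are among them, the share of discontinuers without CVF is (300 − 120)/300 = 60% to (500 − 40)/500 = 92%. That is the group the definition does not reach, not the share left unclassified; those who are suppressed or meet CVF on the next regimen have a class. The 15–25% is also an assumption, and the 2–6% is a range chosen for a precision calculation, not a forecast.

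The conclusion assumes only that the definitions are applied as written and that CVF may be met on the next regimen, as section 6.2 indicates. It is a modest defect in a descriptive secondary item, worth correcting because correction is nearly free.

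**What to change.** In section 7.3.2, define non-response as a VL of 50 copies/mL or more after discontinuation or CVF, with no VL below 50 copies/mL after that event. Keep CVF on the next regimen as its own class, so that a participant who meets both is counted once, as CVF. Report participants with no VL available as a separate line.

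Tabulate the results separately for discontinuation with and without CVF, with all discontinuers in the denominator. This also prevents unclassified or untested participants from dropping out of the suppression proportion.

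The cost is wording and one extra table split. Follow-up duration and VL testing do not change. Extending follow-up only for those whose first VL after switching is 50 or more, and then using their last VL, is not advisable: it would retest only viraemic participants and tilt the result toward suppression.

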Emergent resistance	
 
▪ Proportion of participants with resistance and and proviral DNA testing at discontinuation/CVF.
 
		

Endpoint	Definition
	
 
▪ Proportion of participants with history of resistance and proviral DNA testing prior to discontinuation/CVF.
 
▪ The proportion of participants tested with any resistance mutation will be reported at discontinuation/CVF and history of prior to discontinuation/CVF, as will mutations associated with reduced susceptibility at the class-level and drug-level                             
 
○ All mutations will be reported; specific resistance mutations of interest to CAB+RPV LA can be highlighted and identified using the International Antiviral Society mutations list and Stanford HIV drug resistance database.
 
 
 

Patient-reported outcomes	
Reasons for initiating CAB+RPV LA	
 
▪ Descriptive summary of bespoke questionnaire (2 items) completed at baseline
 

Baseline adherence	
 
▪ Descriptive summary of bespoke questionnaire (7 items) completed at baseline
 

HIV health-related quality of life	
 
▪ Descriptive summary of WHOQOL-HIV BREF (31 items) completed at baseline, month 12 and discontinuation, if applicable
 

HIV treatment-related worries and stigma	
 
▪ Descriptive summary of HIV Treatment-Related Worries (HRW; 4 items) completed at baseline, month 12 and discontinuation, if applicable
 

Treatment-related benefits	
 
▪ Descriptive summary of bespoke questionnaire (7 items) completed at month 12, if applicable
 

Treatment satisfaction	
 
▪ Descriptive summary of HIVTSQs (12 items) completed at baseline and month 12, if applicable
 

Change in treatment satisfaction	
 
▪ Descriptive summary of HIVTSQc (12 items) completed at month 12, if applicable
 

Treatment preference	
 
▪ Descriptive summary of bespoke questionnaire (3 items) completed at month 12, if applicable
 

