**Clinical variables at regimen initiation**

- Number of years since HIV diagnosis
- Number of years since first ART initiation
- HIV subtype where available
- History of previous ARV exposure before CAB+RPV LA
  - Number of core agents experienced
  - Number of ARV classes experienced
  - Duration of last ARV regimen
  - Prior core agent class
- History of previous virologic failure
- History of previous HIV drug resistance and any historical HIV-1 subtype information, where available
- BMI, height, weight
- History of AIDS-defining events
- Veterans Aging Cohort Study (VACS) Mortality Index score
  - Characteristics for mortality index calculation include age, CD4 count, HIV-1 RNA level, Hemoglobin, FIB-4 index, eGFR, HCV status, albumin, BMI, white blood cell count
- ASCVD risk score
  - Characteristics for CVD risk calculation include age, sex, race, total, LDL and HDL cholesterol, systolic and diastolic blood pressure, on

antihypertensive therapy, on a statin, on aspirin therapy, history of diabetes, and smoking status.

- Framingham risk score
  - Characteristics for CVD risk calculation include age, sex, total and high-density lipoprotein cholesterol, systolic blood pressure, antihypertensive therapy, and smoking status.
- Co-infections
  - Hepatitis B co-infection including serology status
  - Hepatitis C co-infection
  - Syphilis infection (ever)
- Comorbidities
  - Autoimmune disease
  - Cardiovascular disease
  - Invasive cancer
  - Endocrine disorder
  - Mental health disorder
    - Depression
    - Anxiety
    - Sleeplessness
    - Suicidality
  - Liver disease
  - Bone disorder
  - Peripheral neuropathy
  - Renal disease
  - Hypertension
  - Substance abuse
  - Non-AIDS–defining malignancies (excluding hepatocellular carcinoma)
  - Any of the above
- Concomitant medications
  - Anticonvulsants
    - Carbamazepine
    - Oxcarbazepine
    - Phenobarbital
    - Phenytoin
  - Antimycobacterials

- Rifampin
- Rifapentine
- Rifabutin
- Glucocorticoids
  - Dexamethasone
- Macrolide or ketolide antibiotics
  - Azithromycin
  - Clarithromycin
  - Erythromycin
- Narcotic analgesic
  - Methadone

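### The secondary endpoint row labelled emergent resistance is defined as any resistance mutation at discontinuation/CVF, so it does not measure emergence on CAB+RPV LA

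*Protocol*

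**What the plan says.** The row "Emergent resistance" in Section 7.3.2 has three items.

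- Testing at the event: "Proportion of participants with resistance and and proviral DNA testing at discontinuation/CVF".
- Testing in the history: "Proportion of participants with history of resistance and proviral DNA testing prior to discontinuation/CVF".
- Results: "The proportion of participants tested with any resistance mutation will be reported at discontinuation/CVF", and the sentence goes on "and history of prior to discontinuation/CVF, as will mutations associated with reduced susceptibility at the class-level and drug-level". A sub-item adds: "All mutations will be reported; specific resistance mutations of interest to CAB+RPV LA can be highlighted".

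Elsewhere the protocol speaks of resistance without calling it emergent. The synopsis lists the outcome simply as resistance. Section 6.2, objective 3, asks for a description of resistance at the event and of "history of resistance and proviral DNA testing before discontinuation/CVF". Section 7.7.1.1 says that historical results will be assessed and that INSTI and NNRTI mutations at discontinuation/CVF will be described. Section 7.3.3 collects, at initiation, "History of previous HIV drug resistance and any historical HIV-1 subtype information, where available".

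**The concern.** Emergence is a change within a person: a mutation seen at failure that was not there before treatment began. The row carries that name, but its numerator is any mutation in anyone tested at the event. A mutation acquired on an earlier regimen, or one in a drug class unrelated to CAB or RPV, meets the rule as well as a new one does.

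Resistance after failure is one of the consequences that readers of this study will look for. Section 5 itself names its development as a risk when doses are missed. A proportion published under this label would be read as the frequency of resistance arising on CAB+RPV LA, and the definition does not support that reading.

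**Working it through.** **Is there a figure to reproduce?** None is given for resistance. The nearest is the precision statement in Section 7.5: at N = 2,000, exact 95% interval widths of 1.28% and 2.13% for failure rates of 2% and 6%. Clopper-Pearson limits give 0.0143 to 0.0271 (width 0.0128) and 0.0500 to 0.0713 (width 0.0213), so both reproduce. They concern CVF and serve here only for scale: 2,000 × 0.02 = 40 and 2,000 × 0.06 = 120 CVF cases.

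**Does any item test for a new mutation?** No. Two items count testing and the third counts any mutation. None sets a condition relative to the first injection, which Section 7.7.1.1 defines as the index.

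**Does eligibility remove earlier mutations?** Only in part. Section 7.2.2 excludes prior virologic failure on NNRTI or INSTI agents, where data exist, and does not list mutations. Section 7.3.1 requires use per label, which should reduce carriers of mutations relevant to CAB or RPV. Other drug classes are not covered, participants are treatment-experienced, and Section 7.7.1.1 expects to count some with a history of INSTI or NNRTI resistance.

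**Does the parallel history figure supply the missing comparison?** Let p1 be the proportion with a mutation at the event and p0 the proportion with one in the history, in the same people. The share with a mutation at the event and none in the history is bounded only by

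max(0, p1 − p0) ≤ share ≤ min(p1, 1 − p0).

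The documents give neither p1 nor p0. As an illustration, assume p1 = 50% and that every CVF case has both results:

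| Assumed p0 | Bounds on share | Of 40 CVF (20 with a mutation) | Of 120 CVF (60 with a mutation) |
|---|---|---|---|
| 10% | 40% to 50% | 16 to 20 | 48 to 60 |
| 20% | 30% to 50% | 12 to 20 | 36 to 60 |
| 30% | 20% to 50% | 8 to 20 | 24 to 60 |

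The upper bound equals p1 in every line, so no overstatement at all is also compatible with the two proportions. They do not identify the share that matters.

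**Is the history a pre-treatment baseline?** Not as worded. It covers everything before discontinuation/CVF. CVF usually needs two consecutive viral loads of at least 200 copies/mL, so a genotype taken on treatment at the first of them could fall into history. Even a paired comparison with that history could then miss a truly new mutation. Historical results also exist only where available, so the two proportions may come from different people.

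**Which events are counted?** Section 5 describes resistance among virologic failures with test data. The row is triggered by discontinuation or CVF, and discontinuation in Section 7.3.2 includes a physician-confirmed switch or stop with no viral load condition. Section 7.1 selects sites that test at discontinuation as well as at failure. Discontinuations without failure can therefore enter, and the row does not separate proviral DNA from other results.

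**The case against.** The strongest reply is that only the label is at fault. The word emergent appears once, as the row's name. The objective, synopsis and analysis section ask for resistance at the event and history, and the row delivers that. History is part of the endpoint, so earlier mutations are displayed and not hidden. Results are held by participant identifier and all mutations are to be reported, so a paired table could be made, and an analysis plan that is not shown may contain one. The endpoint is secondary in a study with no formal hypothesis.

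Much of this stands. A reader might infer that the protocol commits to reporting earlier or archived mutations as having arisen on CAB+RPV LA. It does not say so, and the history clause counts against that reading. A reader might also infer that results at a suppressed discontinuation would be mainly proviral DNA; the documents do not say which assay would be used. Nor does the row state that CVF and other discontinuations must share one denominator.

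What does not stand is leaving the matter to the analysis plan. The protocol has fixed a definition under this name. A plan that follows it produces a figure that is not emergent resistance, and one that adds a paired rule departs from it.

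**Conclusion.** The point holds as a mismatch between name and definition. The row measures any resistance among those tested at discontinuation/CVF, with history alongside, and cannot show what emerged on treatment.

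In the same tested people, any mutation can never be less frequent than a new mutation, so the figure can overstate emergence. Mixing in discontinuations without CVF changes the denominator too, and could move the proportion either way relative to one among failures.

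It is tempting to attach an inflation factor. The documents do not support one: they give no frequency of earlier or new mutations, and any factor would rest on assumed values and on an assumed relation between the two. The bounds above show only that the quantity is not identified.

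The consequence is confined to one secondary descriptive endpoint. Primary objectives and study size are unaffected.

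**What to change.** 1. Keep the present items and rename the row *Resistance at discontinuation/CVF*.
2. Add emergent resistance as a separate item: a mutation detected at CVF and absent from all of the same participant's results obtained before the first injection. The denominator is CVF cases with results at both times.
3. Show CVF cases with no result before first injection as *origin unknown*.
4. Show discontinuations without CVF, and proviral DNA results, separately.

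The cost is one endpoint row and one added table. Event results and history are already to be collected where testing was done. The eCRF must hold the date and specimen type of each result; the protocol does not say whether it does. The main downside is a smaller denominator: of the 40 to 120 CVF cases implied by Section 7.5, only those with an earlier test contribute, and many may fall under origin unknown. If that is judged too few to be useful, step 1 alone removes the mislabelling.
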